MTD: Maximum Tolerated Dose **ID: Intolerant Dose** No prokinetic response MTD ID Day10 Day13 Subject Day 1 Day4 Day7 Day16 Day19 Day22 Day 25 25mg 50mg 100mg 75mg >125mg 150mg 175mg 2 25mg 50mg 75mg 100mg 125mg 150mg 175mg 200mg Stage 1 Period 2.1 3 50mg 75mg 100mg 125mg 150mg 175mg 25mg (COHORT 1) 4 25mg 50mg 75mg 100mg 125mg 150mg Single dose 125mg 5 25mg 50mg 100mg 150mg 75mg 175mg 200mg safety, 50mg 100mg 125mg 6 75mg 25mg tolerability and 50mg 100mg 7 25mg 75mg 125mg 150mg 175mg identification of 8 25mg 50mg 75mg 100mg 125mg 150mg prokinetic dose 50mg 100mg 125mg 150mg 25mg 75mg → 175mg 200mg 10 25mg 50mg 75mg 100mg 125mg 150mg 175mg 200mg STDE DOSE in this example is 75 mg, that being the lowest dose that is safe and tolerable in all subjects and has a prokinetic effect in at least some

Schematic for Stage 1, Period 2.1: Hypothetical dosing regimens

Pharmacokinetics: Timed blood samples (5.0 mL) will be collected into Li-Heparin treated tubes for analysis of ENT-01 plasma concentrations. Plasma samples will be obtained for pharmacokinetics before dose administration and at 1, 2, 4, 8, and 24 hours.

Once collected, PK samples will be stored in a -20°C or -70°C freezer until time of shipment. Labels and appropriate shipping materials will be provided to sites. The concentration of study drug will be determined from the plasma samples using a validated analytical method. Details of the method validation and sample analysis will be included with the final clinical study report.

Individual stopping criteria:

The complete panel of Blood Chemistries described in Appendix 1 are to be drawn 24 hours after each dose. Results will be reviewed the evening before the following dose. In addition, any patient with at least 1 DLT endpoint (see **Section 9.8**), or with another non-DLT gastrointestinal AE > grade 3 that is at least possibly attributable to ENT-01, or elevated AST, ALT, or total bilirubin > 3x ULN or a reduction of body weight of 10% or more from baseline will be terminated. ENT-01 has very little systemic absorption, and hence adverse events are expected to be within the gastrointestinal system.

Refer to Section 9.12 for Adverse Event Grading and to Section 9.8 for DLT Endpoint

Criteria.

Go/No-go decision:

Safety: We are assuming that no more than 1 patient out of ten (10%) will have an adverse event

of grade 4 or 5 that is at least possibly related to ENT-01 in dose levels thought to be below

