CP1001 v0.9, Version Date: 27JUL2017

[figure not shown]
31

kept on that fixed dose for a further 2-4 dosing days (3 days if it falls on a Saturday, 4 days if it falls on a Sunday).

The sentinel group will be a group of 10 patients who did not participate in Stage 1. Patients will be given three consecutive doses of the dose which was found to be safe and tolerable in everybody (STDE) and effective in at least some patients in Stage 1 (75 mg in schematic) at home. Patients will self-administer the study medication *daily* for 3 doses (3 days at each dosing level). The dose will be taken upon awakening on an empty stomach along with 8 oz. of water simultaneously to dopamine). The patient will not be allowed to ingest any food for at least 60 minutes after study medication. The daily diary will be completed and results verbally transmitted and emailed to the study coordinator every evening including on week-end days and entered into the electronic data capture system the same night or first thing in the morning. The coordinator will check in with the patients daily, at the end of the day and determine whether there have been any adverse events or CSBM. If the patient has not produced a CSBM within 24 hours of a dose, on at least two of the three days at a given dose, then the patient will be told to proceed to the higher dose of STDE+25mg (eg. 100mg qd) and also to use a suppository followed by an enema if necessary on the evening of the third day (See rescue diagram below). At the end of the second dosing period (100mg for 3 days), the same criteria will be applied to make a determination as to whether to proceed to STDE+50mg (e.g. 125 mg qd) or not. The incremental dosing will continue up to the consistently clinically effective (pro-kinetic) dose, or to the DLT, whichever comes first. Patients who do not have pro-kinetic effect at DLT will be treated with the highest dose at which they did not have a DLT, if it is at least the STDE dose; if the DLT occurred at the STDE dose, then the patient will be terminated. Should a pro-kinetic response not occur at 175 mg, patients will take 175 mg for the 2-4 additional fixed-dose dosing days and 6 randomized dosing days (assuming randomization is to treatment). DLT will be the dose inducing repeated vomiting or diarrhea within 24 hours of dosing. The lowest dose producing a CSBM on 2/3 consecutive doses will be noted as the pro-kinetic dose (LSTDEi i.e. consistently clinically effective safe and tolerable dose for that particular individual). Patients will be kept on the lowest dose producing a pro-kinetic effect for another 2-4 days prior to randomization in Period 4. The Enterin CMO will review the stool diaries prior to randomization to ensure dosing adequacy. PAC-QOL and PAC-SYM will be repeated prior to randomization at Visit 3. CSBM during the fixed dose period will

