
be calculated as CSBM/#fixed dose days x 7. The primary end-point is obtained by comparing this number to the baseline CSBM obtained at the end of the run-in period.

2: SUPPOSITORY/ENEMA RESCUE USE DURING DOSE ESCALATION IN STAGE

Patients will wear I-Buttons starting with the lowest dose (e.g. 75 mg) and will remove them on day 5 of the wash-out period. The remaining 30 patients will start on STDE (e.g. 75mg) as soon as they have completed the Run-in Period and will follow the same incremental dosing regimen until they reach their LSTDEi or maximum tolerated dose. These regimens and adjustments are shown in the schematic below.

Once the LSTDEi has been established, each patient will remain on that dose for two to four additional days prior to randomization in Period 4 (5 to 7 consecutive days on prokinetic dose)

N.B. Primary end-point is obtained by comparing stool diary at this point with baseline diary on rescue medication at the end of the run-in period.

Visit 3 for non-PK patients (Day before Randomization).

Non- PK patients will come to the site for a visit to return any unused study drug (B), receive 6 daily doses of randomized drug (A or C), Sitzmarks capsules and will complete all the questionnaires listed below. They will be sent home with 6 daily doses of A or C and Sitzmarks capsules and will return for Visit 4 on Day 6 of randomization to complete all the questionnaires.

Go/No-go decisions:

Safety: We are assuming that no more than 1 patients out of forty (2.5%) will have an adverse event of grade 4 or 5 that is at least possibly related to ENT-01 in this Stage. Should there be more than 1 patient with an AE grade 4 or 5 that is at least possibly related to Enterin-0 in this cohort

of 40 patients, the study will be put on an immediate safety hold until an emergency DSMB meeting can be held to evaluate the study for possible discontinuation.

Tolerability: We are assuming that all patients will exhibit a pro-kinetic effect at a dose lower than DLT and less than or equal to 175mg. Patients reaching DLT before a pro-kinetic effect will be terminated if the highest dose for the patient without a DLT was the STDE dose. Otherwise the patient will be treated at the highest dose at which they did not experience a DLT if they are randomized to the treatment arm (or will receive the equivalent dose of placebo).

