Efficacy: We are assuming that a consistent pro-kinetic effect will be observed in all patients. Patients in whom a pro-kinetic effect is not observed at the maximum dose of 175mg will continue to take 175mg for another 2 days and enter the randomized period. If they are randomized to treatment, they will be given 175mg/day for the 6 randomized dosing days.

Individual stopping criteria:

Patients who reach DLT before a pro-kinetic effect, exhibit LFT elevation above 3xULN, have a 10% or greater reduction in body weight or those with a non-DLT gastrointestinal AE > grade 3 within 24 hours of taking ENT-01 that is at least possibly attributable to ENT-01 will be terminated.

Pharmacodynamics: Patient will record bowel movements, ease of passage, consistency and suppository usage in the daily diary throughout the Period and transmit the information to the coordinator every evening.

Sleep assessment: Patients will wear the I-Button throughout the dosing period and remove it only during bathing periods.

STDE DOSE in this example is 75 mg, that being the lowest dose that is safe and tolerable in all subjects and has a prokinetic effect in at least some LSTDEi is the lowest safe and tolerable dose that produces a prokinetic response reached by an individual in at least 2 of 3 days at that dose Subject Day1 Day2 Day3 Day4 Day5 Day6 Day7 Day8 Day9 Day9 Day1 Day12 Day12 Day13 Day14 Day15 Day16 Day17 Day18 Day19 Day20 Day21 Day22 100mg 100mg 100mg 100mg 100mg 100mg 100mg ng 100mg 100mg 100mg 100mg 100mg 100mg 100mg 100mg 125mg 125mg 125mg 125mg 125mg 125m 150mg 150mg 150mg 150mg 150mg 150mg 150mg COHORT 1, 100mg 100mg 100mg 100mg 100mg 100mg Stage 2. SENTINEL PERIOD 3.2, g 125mg ng 150mg 150mg 150mg 150mg 150mg 150mg ROUP N=10 (COHORT 1) 75mg | 75mg | 75mg Safety and tolerability of 3 day dosing. and extension to a total of 5 COHORT 2 doses GROUP, N=32 **RUN-IN PERIOD FOR SUBJECTS 11-40** Day 23 Day24 Day25 Day26 Day27 Day28 Day29 Day30 Day31 Day32 Day 33 Day34 Day35 Day36 Day37 Day38 Day39 Day40 Day41 Day42 Day43 Day44 COHORT 2 GROUP, N=32 11-40

Schematic of Stage 2, Period 3.2 with hypothetical dosing regimen

DSMB: The DSMB will meet at the end of the fixed dose period for the ten sentinel patients.

LSTDEI LSTDEI LSTDEI LSTDEI

PERIOD 4

(Stage 2): Randomized, double-blinded treatment period to determine the effect of orally administered ENT-01 on pharmacodynamics and motility.

Duration: 6 days

Visit 3 for PK patients (Day 1 of randomization):

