PK subjects will come to the site on Day 1 of randomization ON AN EMPTY STOMACH and return their unused study drug at that time point. They will receive the first dose of medication at the site following the first PK blood draw, and complete the questionnaires listed below. PKs will also be performed at 1, 2, 4, and 8 hours post-dose. A sample for liver function tests will be drawn with the 8-hour post-dose PK draw. They will receive 4 daily doses to take home, then return on Day 6 to receive their 6th dose at the site after their first PK draw of the day. PKs will again be obtained post-dose at 1, 2, 4 and 8 hours, a sample for liver function tests will be drawn with the 8-hour post-dose PK draw, and all the questionnaires completed.

Following the 5-7 day course on the pro-kinetic dose, ALL patients will be randomized to drug or placebo and enter Period 4. Randomization will be 1:1 to treatment vs. placebo. Randomization will occur in accordance with the randomization schedule generated by [name] at Weill-Cornell Medical College. Patients and study staff will be blinded to actual study treatment and will remain blinded throughout the remainder of the study. BDI, MMSE, Trail making A and B, NMSQ, UM-PDHQ, PFS-16, RBDQ, PDSS, PAC-SYM and PAC-QOL will be administered prior to randomization. The UPDRS will be administered and weight and vital signs will be taken).

Assuming randomization is to treatment group, the patient will remain on that dose daily for a 6 day period (6 dosing days). Patients randomized to placebo will be switched to the same number of placebo tablets as they were taking prior to switching. All patients will continue to keep daily diaries during this period. The use of rescue medication (suppositories and enemas) for constipation will be permitted as needed if a bowel movement has not occurred for 3 days and recorded in the diary. Patients will be contacted daily. The suppository will be taken on the evening of the third day as shown in Figure 1 above. *Any bowel movement produced as a result of rescue medication will not be counted.*

Patients reaching their tolerability limit at a dose lower than a clinically effective dose (STDE) will be terminated from the study. We have included 40 patients in this Stage to allow for 15% drop-outs for reasons including tolerability.

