10 DATA MANAGEMENT AND STATISTICS

This is a trial with two stages. The Stage 1 portion will consist of 10 patients who will be dose escalated in single doses. Each patient will proceed through all the dose escalations starting at 25 mg and ending at 200 mg or at the dose at which s/he experiences a dose limiting toxicity (DLT). The doses to be tested are 25mg, 50mg, 75mg, 100mg, 125mg, 150mg, 175mg and 200mg. In the Stage 2 portion, all patients will go through a multiple dose escalation (3 dosing days at each dose) and the dose at which the patient experiences a consistent pro-kinetic effect (spontaneous, complete stool in at least 2/3 consecutive doses) without a DLT will be the dose for that patient. Patients who experience a DLT prior to reaching their pro-kinetic dose and at a dose equal to or less than the STDE dose will be terminated. Otherwise the patient will be assigned the highest dose at which they did not experience a DLT. If the patient reached 175 mg without a DLT and without a pro-kinetic dose, her/his dose will be 175 mg. The primary endpoint for the Stage 1 study is to determine whether the dose levels explored are safe and tolerable. The primary endpoint for the Stage 2 study is the regularization of bowel function as determined by stool frequency at the end of the fixed dose period compared to baseline. The Stage 2 portion will enroll 40 patients, with a target sample size of 34 evaluable patients. Six extra patients are enrolled to allow for patient withdrawals or terminations prior to the completion of the trial.

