10.1 Sample Size/Power Considerations

10.1.1 Stage 1

There will be 10 patients enrolled in Stage 1. Two patients will be started on the 25mg dose. If no DLTs are observed, they will be escalated to the next dose and the remaining 8 patients will be started at 25mg. Each dose level will be a single dose and patients will be observed for three days before being given the next higher single dose. It is intended that each patient receive a single dose of each of the levels: 25mg, 50mg, 75mg, 100mg, 125mg, 150mg, 175mg and 200mg. However, if a patient experiences a DLT, they will not be further escalated.

A DLT is defined in Section **9.8** using the Common Terminology Criteria for Adverse Events (CTCAE), as a grade 2 vomiting within 24 hours of taking ENT-01 grade 2 diarrhea within 24 hours of taking ENT-01, grade 2 abdominal pain within 24 hours of taking ENT-01, grade 2 postural hypotension within 24 hours of taking ENT-01. Additionally, an LFT elevation > 3xULN within 24 hours of taking ENT or any gastrointestinal AE > grade 3 within 24 hours of taking ENT-01 that is at least possibly attributable to ENT-01 will be considered dose-limiting toxicity for the purpose of analyses.

There is no power calculation for the Stage 1 portion because it is merely trying to determine whether ENT-01 is safe and tolerable for these levels. The PK analyses will be descriptive and are meant to understand how ENT-01 is metabolized.

10.1.2 Stage 2

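### A Stage 2 patient with a DLT above the STDE and no pro-kinetic response is stepped down under two passages of the protocol, terminated under a third, and handled one dose level off by a fourth

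*Protocol*

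**What the plan says.** Four places in the July 2017 protocol govern a Stage 2 patient who meets a DLT before showing a pro-kinetic effect, and a fifth sentence touches on it.

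- **Section 3.1, Period 3.2, dosing text.** The patient "will be treated with the highest dose at which they did not have a DLT, if it is at least the STDE dose". Termination is reserved for a DLT at the STDE itself.
- **Section 10, opening paragraph.** The same rule. A DLT at or below the STDE ends participation: "STDE dose will be terminated. Otherwise the patient will be assigned the highest dose at which they did not experience a DLT".
- **Section 3.1, Period 3.2, Go/No-go decisions, Tolerability.** "Patients reaching DLT before a pro-kinetic effect will be terminated if the highest dose for the patient without a DLT was the STDE dose". Anyone else goes on at the highest DLT-free dose, or matching placebo, after randomization.
- **Section 3.1, Period 3.2, Individual stopping criteria.** "Patients who reach DLT before a pro-kinetic effect, exhibit LFT elevation above 3xULN", or meet the weight-loss or gastrointestinal AE criterion, are terminated. No dose condition is attached to the DLT criterion, and there is no cross-reference to the dosing text.
- **Section 3.1, Period 4.** "Patients reaching their tolerability limit at a dose lower than a clinically effective dose (STDE) will be terminated from the study".

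The SAP does not choose between them. SAP Section 2.1 describes only the dose carried forward when a pro-kinetic effect occurs without a DLT.

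**The concern.** These instructions cover the same patient in the same period and cannot all be followed. Protocol Section 12.10 requires exact adherence and allows no waivers, and nothing says which passage prevails. A coordinator looking for the stopping rule would naturally go to the paragraph with that heading, which is the one that departs furthest from the dosing text.

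Two things are at stake. The first is whether a patient continues on ENT-01 after a dose-limiting event. The second is whether that patient reaches the end of the fixed-dose period. Protocol Sections 10.1.2 and 10.5 and SAP Section 7.7.2 take the primary success assessment at that point.

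The likely origin is Stage 1. There, the paragraph under the same heading terminates "any patient with at least 1 DLT endpoint", and Section 10.1.1 says that "if a patient experiences a DLT, they will not be further escalated". In Stage 1 these are compatible, because dosing is a single ascending series with no step-down. In Stage 2 the dosing text adds a step-down, and the stopping criteria do not reflect it. That origin is an inference; the conflict does not depend on it.

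**Working it through.** **Inputs.** Example STDE of 75 mg (Section 3.1 schematics and dosing text). Stage 2 doses rise in 25 mg steps to 175 mg (Section 3.1; SAP Section 2.1), which gives five levels: 75, 100, 125, 150 and 175 mg. In every row the patient has had no pro-kinetic effect when the DLT occurs.

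| DLT at | Dosing text and Section 10 | Tolerability paragraph | Individual stopping criteria | Stop/continue conflict |
|---|---|---|---|---|
| 75 mg | Stop | Falls under its otherwise clause, but no DLT-free dose exists | Stop | No, but one rule is unusable |
| 100 mg | Continue at 75 mg | Stop (highest DLT-free dose is the STDE) | Stop | Yes |
| 125 mg | Continue at 100 mg | Continue at 100 mg | Stop | Yes |
| 150 mg | Continue at 125 mg | Continue at 125 mg | Stop | Yes |
| 175 mg | Continue at 150 mg | Continue at 150 mg | Stop | Yes |

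**Count.** There is a conflict at 4 of 5 levels: 1 level (100 mg) where the Tolerability paragraph and the stopping criteria oppose the dosing text and Section 10, and 3 levels (125 to 175 mg) where the stopping criteria stand alone.

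**The off-by-one.** If the highest DLT-free dose was the STDE, the DLT came at STDE + 25 mg. The Tolerability condition therefore catches the patient one level above the one the dosing text means to stop, and misses the patient with a DLT at the STDE.

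**Period 4 sentence.** Stage 2 starts at the STDE, so no one is dosed below it. The sentence is either empty or a loose restatement of the dosing-text rule, so it does not settle the question.

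**Effect on numbers.** Spare patients: 40 − 34 = 6. A patient terminated without an end-of-fixed-dose assessment would use one of them.

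The plan's power figure, checked first: an exact binomial test against 0.10 with upper tail at most 0.025.
- N = 34: reject at 8 or more successes; power at 0.29 is 0.812.
- N = 40: reject at 9 or more; power at 0.27 is 0.791.

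Both agree with the stated 80%. If all losses, these included, stay within the six spares, N lies between 34 and 40 and power at 0.29 lies between 0.788 (N = 37) and 0.861 (N = 36 or 40). If such losses came on top of the planned six, power at 0.29 would be 0.751 at N = 32, 0.677 at N = 30 and 0.744 at N = 28. The number of such patients is not given, so these values are illustrations, not forecasts.

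**The case against.** **Shorthand.** The stopping criteria follow closely on the Tolerability paragraph and reuse its phrasing, so they could be read as a summary of a conditional rule stated in detail elsewhere. For a DLT at 125 to 175 mg, the three detailed passages do agree. This does not rescue the text. The criterion carries no condition, and the nearest conditional rule itself contradicts the dosing text and Section 10 at STDE + 25 mg.

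**Few or no such patients.** The Tolerability paragraph assumes that every patient will respond below the DLT and at no more than 175 mg. The Period 4 text says that the 40 patients allow for 15% drop-outs, tolerability included. Both points stand. The rule is a contingency, and losing some patients to it is already budgeted.

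**Safety is bounded.** This also stands. The Section 9.8 thresholds are Grade 2 events, and the DLT sentence in the Period 3.2 dosing text is narrower still (vomiting or diarrhea). The step-down dose is lower and caused no DLT. The liver, weight and gastrointestinal stops, withdrawal on clinical judgment (Section 4.5) and DSMB monitoring (Section 9.21) all remain.

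**Bias in the primary result.** A reader might infer that terminated patients would leave the primary analysis as failures and so inflate the success rate. The documents do not support that. The SAP supersedes the protocol's statistical considerations (SAP Section 1), and its full analysis set (SAP Section 6.3) needs only a baseline and one post-baseline stool diary assessment, so a terminated patient can remain in it. Whether that patient enters the success proportion depends on the end-of-fixed-period assessment (SAP Section 7.7.2) and on the rule of no imputation and non-missing denominators (SAP Section 7.1). Exclusion is possible, not certain.

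Nor is a patient without a pro-kinetic dose necessarily a primary failure. As an illustration, one CSBM day in four diary days gives 1/4 × 7 = 1.75 per week. Against a baseline of one in fourteen, 1/14 × 7 = 0.5, the rise is 1.25, which meets the success criterion.

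**Conclusion.** The inconsistency is real and should be fixed. The protocol's rules for a DLT before response give opposite instructions at 4 of 5 dose levels when the STDE is 75 mg, and one of them leaves a DLT at the STDE with no dose to assign. The count rests on the July 2017 wording and the example STDE.

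The consequences are limited. The protocol expects no such patients, the safety risk is bounded, and the effect on the success rate is undetermined because no DLT rate is given and the SAP's analysis set may retain those who stop. A reader might infer that the trial's power is threatened. Within the planned allowance of six losses it stays close to the intended 80% or above, and nothing in the documents points to losses beyond that. A reader might also try to total the extra drug exposure of a stepped-down patient. The duration would have to be assumed, because the dosing schematic is not legible in the text available, so no exposure figure is put forward.

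The text of the February 2018 amendment is not among the documents. SAP Section 2.1 says that it changed the Stage 2 dose range, removed randomization and changed nothing else. That suggests the conflict persisted but does not prove it.

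**What to change.** Use the rule in the Period 3.2 dosing text and Section 10 everywhere.

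1. **Tolerability paragraph:** make the termination condition *if the DLT occurred at the STDE dose*.
2. **Individual stopping criteria, Period 3.2:** make the first criterion *reach DLT at the STDE dose before a pro-kinetic effect*. Keep the liver, weight and gastrointestinal AE criteria unchanged.
3. **Period 4 text:** replace the tolerability-limit sentence with a cross-reference to that single rule.
4. **February 2018 amendment:** confirm that it carries the same rule.

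If the sponsor and DSMB prefer the stricter rule, the dosing text, the Tolerability paragraph and Section 10 should be changed to match it instead; what matters is that one rule applies.

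The cost is wording in three places, made through a protocol amendment with IRB approval and submission to the FDA before implementation (Protocol Sections 9.23 and 12.9). It needs no extra patients, visits or data, and no sample-size figure changes.
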